6.2. Outcome derivation

Primary outcome is the mean of all 5 sub-scores (symptoms, pain, activity of daily living, sport and quality of life) assessed at 24 months postoperatively.

Secondary outcomes MOCART and 3D MOCART scores at 3, 12, 24 months after surgery will be calculated from MRIs carried out at follow-up visits. The relative delta R1 will be evaluated by dGEMRIC and recorded at 3, 12, 24 months follow-up visits and referenced to the native cartilage of the treated knee based on MRI.

6.3. Analysis methods

6.3.1 Primary analysis

The primary analysis will be done on the PPS. Missing data will be handled according to section 6.4. Primary objective is to demonstrate in patients younger than 65 years with articular knee

cartilage injuries the superiority of N-TEC to N-CAM, assessing by KOOS measured 24 months after surgery.

The primary endpoint will be analyzed with a linear mixed effects model, including therapy (N-TEC vs. N-CAM; categorical variable) as single explanatory variable (fixed effect), and including study center as random effect variable to account for the multicenter study design.

As a sensitivity analysis, we will analyze the primary endpoint by adjusting for covariates and testing for interactions. The linear mixed-effects model will include therapy (N-TEC vs. N-CAM; categorical variable), onset of symptoms (stratified categorical: acute: ≤ 1 years; chronic: > 1 years) and the covariate baseline KOOS (continuous variable) as explanatory variables (fixed effects). In addition, the model will include the interaction between therapy and onset of symptoms. A significant interaction would indicate that the outcome of the therapy depends on how long the symptoms have been present. Further, study center will be included as a random effect variable in the model to account for the multicenter study design.

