6.2 Methods of minimizing bias

6.2.1 Randomization

A permuted-block (2, 4 and 6 size) randomisation method will be performed. This method will prevent confounding of the treatment effect with "disease duration". For each centre there will be a randomisation list. The list will be generate by Sealed Envelope online software application (https://www.sealedenvelope.com/) and provided to database manager in order to implement and allow the automatic group assignation.

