7.1 Eligibility criteria

Participants fulfilling all of the following inclusion criteria are eligible for the study:

- Patient is □18 and □65 years old at time of screening.
- Patient has a localized articular cartilage defect of the femoral condyle and/or the trochlea and/or patella of the knee. 2 localized cartilage defects are accepted if the total defect size is □ 8 cm², both cartilage defects are located at the femoral condyle and/or the trochlea and/or patella and both cartilage defects are to be treated with N-CAM or N-TEC.
- Patient has a defect of grade 3 or 4 according to the ICRS classification.
- Patient has a defect size □2 and □8 cm² as assessed by MRI/arthroscopy.
- Patient has an opposite intact (□CRS Grade 2) articulating joint surface (no "kissing lesions").
- Patient has an intact meniscus (maximum 1/2-resection).
- Patient has a stable knee joint or sufficiently reconstructed ligaments. If not, ligament repair has to be done during the operation or within 6 weeks of the planned cartilage treatment.
- Patient has a maximum baseline score of 75/100 in the KOOS subjective knee evaluation.
- Patient is willing and able to give written informed consent to participate in the study and to comply with all study requirements, including attending all follow-up visits and assessments and to complete postoperative rehabilitation regimen.

The presence of any one of the following exclusion criteria will lead to exclusion of the participant:

- Patient is the investigator or any sub-investigator, research assistant, pharmacist, study
 coordinator, other staff or relative thereof directly involved in the conduct of the protocol or in a
 dependency or employment with the sponsor.
- Patient is unable to understand the patient information
- Patient is unable to undergo magnetic resonance imaging (MRI) or is sensitive to gadolinium
- Patient has had prior surgical treatment of the target knee within 12 months using
 mosaicplasty and/or microfracture (Note: prior diagnostic arthroscopy with debridement and
 lavage are acceptable within 12 months). Anterior cruciate ligament repair is accepted, if the
 target knee is stable or a primary ACL reconstruction is performed within 6 weeks of the
 planned cartilage treatment.
- Patient has free range of motion of the affected knee joint or □ 10° of extension and flexion loss.
- Patient has a relevant meniscus tear. Partial meniscal removal allowed, if not exceeding 1/2.

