9.2.3 Assessment of other outcomes of interest

Retrospectively the data collected in the primary and secondary outcome will be used for analysis with regard to the onset of symptoms. The patients will be classified regarding the onset of symptoms as acute (onset < 2 years) or chronic (onset > 2 years) and differences between the treatment groups as well as within the treatment groups will be analyzed in order to identify possible correlation between the efficacy of the IMP treatment and the time of onset of symptoms.

In addition a subgroup analysis to compare the outcome with regard to the localization of the defect (patella vs. femoral condyle/trochlea) will be performed in order to evaluate, how the outcome of patella defects, which are known to have an inferior clinical outcome in standard therapies, is in case of treatment with N-TEC and N-CAM.

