2.2. Randomisation

Upon enrolment in the study, patients will be given a patient ID and entered into the database myclinicaldata (Medacta) by the PI or designated persons of the respective center. Patients will be randomized to the N-TEC (mature tissue) or N-CAM (immature tissue) group.

A permuted-block (2, 4 and 6 size) randomization method will be performed. A randomization list will be associated to each center, guaranteeing an equal distribution of the two groups in all the centers (center stratification). The list is generated by Sealed Envelope online software application (<https://www.sealedenvelope.com/>).

After the screening phase, patients will be allocated to the randomization group through the electronic data capture (EDC) system, which automatically links the patient to the group correspondent to the free available slot of the randomization list, previously uploaded to the system.

The generation of the sequence from sealed envelope website and its upload into the EDC system, will be managed by the owner of platform, who is not involved in clinical center activities (patient selection, clinical visits, radiological evaluation). The clinical centers personal does not have access to the randomization sequences.

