6.3.1.2. Analysis of secondary endpoints

The following secondary endpoints will be analyzed:

- KOOS score at 12 months after surgery
- relative GAG-content (rel. $\Delta R1$) by delayed gadolinium-enhanced MRI of cartilage (dGEMRIC) 3, 12 and 24 months after surgery
- MOCART score at 3, 12 and 24 months after surgery
- EQ-5d score at 12 and 24 months after surgery

All secondary endpoints will be analyzed with a linear mixed effects model as described for the sensitivity analysis of the primary endpoint (with the corresponding baseline scores as covariate). If necessary, endpoints will be transformed in order to fulfill assumption of a normal residual distribution, or, if no reasonable transformation can be found, generalized linear mixed-effects models will be applied.

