7.3. Sensitivity analysis

We found that the distribution of KOOS at the time of outcome had the pattern of a ceiling effect in both treatment arms (Fig 1), even more pointed in the N-TEC group. Thus, the median (solid line) is a better summary measure than the mean (dashed line).

Figure 1. Distribution of primary outcome

[figure not shown]

Figure 1. Distribution of primary outcome

Hence, we decided to use median regression models to derive treatment effect with standard errors (SE) estimated based on bootstrapping with 5000 repetitions. We chose bootstrapped SEs to avoid 95% CIs exceeding 100, since there are no data points over 100 to bootstrap from. We furthermore adjusted for baseline KOOS score to gain precision of the treatment effect, given that the outcome is derived from self-ratings and dropped center as random effect.

8. References

2. <http://www.consort-statement.org/consort-2010>
3. Rubin DB. Multiple **imputation for nonresponse** in surveys. New York: John Wiley & Sons; 2004.

[name], the 28th of November 2022

A handwritten signature in blue ink that reads "[name]".

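### The primary KOOS model leaves out baseline KOOS, so precision is given up and no specified analysis reports a baseline-adjusted overall mean difference

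*SAP*

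**What the plan says.** Protocol 11.4.2 and SAP 6.3.1 give the same primary model: linear mixed, "including therapy (N-TEC vs. N-CAM; categorical variable) as single explanatory variable (fixed effect"), random centre. Baseline KOOS enters a mean model for 24-month KOOS only in the sensitivity analysis, together with onset of symptoms and a therapy-by-onset interaction.

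Elsewhere the plan treats baseline differently:

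- Protocol 7.1 makes it an entry condition: "Patient has a maximum baseline score of 75/100 in the KOOS subjective knee evaluation". Protocol 9.3.2 schedules the questionnaire before randomisation.
- SAP 6.3.1.2 analyses the listed secondary endpoints, 12-month KOOS among them, "as described for the sensitivity analysis of the primary endpoint (with the corresponding baseline scores as covariate").
- SAP 7.3 reports that "We found that the distribution of KOOS at the time of outcome had the pattern of a ceiling effect in both treatment arms", moves to median regression without the centre effect, and says: "We furthermore adjusted for baseline KOOS score to gain precision of the treatment effect".

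On allocation, Protocol 6.2.1 says of the permuted blocks: "This method will prevent confounding of the treatment effect with" disease duration. SAP 2.2 describes one list per centre, "guaranteeing an equal distribution of the two groups in all the centers (center stratification").

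**The concern.** The endpoint that decides the trial is the one KOOS analysis that ignores a prognostic value already collected for every eligible patient. The documents give no reason for this, and SAP 7.3 states the argument against it.

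The other specified analyses do not fill the gap. The sensitivity model adjusts for baseline, but with reference coding its therapy coefficient is the effect in a single onset category, and no average over categories is named. The SAP 7.3 model targets a difference in medians, whereas the trial was sized on means. A reader who wants the baseline-adjusted overall mean difference will not find it specified anywhere.

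At stake are the width of the confidence interval and the ability to correct this one trial for a chance difference in baseline KOOS. Bias is not at stake.

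The sentence in Protocol 6.2.1 compounds the matter. Blocks within centre balance arm sizes within centre. They do not balance symptom duration.

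**Working it through.** **Inputs from the documents (Protocol 11.2, SAP 2.3 and 4.2).** N-CAM mean 75, N-TEC mean 85 (10-point effect), SD 17, values capped at 100, two-sided t-test at 5%, 97 evaluable, 10% drop-out.

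**Step 1: reproduce the plan's figure.** For a normal variable capped at 100, with a = (100 − μ)/σ, the mean is μΦ(a) − σφ(a) + 100(1 − Φ(a)).

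- N-CAM: a = 25/17 = 1.47, mean 74.47, SD 15.97.
- N-TEC: a = 15/17 = 0.88, mean 83.24, SD 14.31.
- Difference 8.77; pooled SD √[(15.97² + 14.31²)/2] = 15.16.
- SE = 15.16 × √(4/97) = 3.08; noncentrality 8.77/3.08 = 2.85.
- Power 80.5% by the noncentral t, 80.1% by simulation. Recruitment 97/0.9 = 107.8, so 108.

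The stated 97, 108 and 80% are right for the unadjusted test.

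**Step 2: is the unadjusted model valid?** With no true difference, r = 0.4 and the cap at 100, simulated type I error was 5.4% unadjusted and 5.2% adjusted (4,000 replicates, Monte Carlo SE about 0.35 points). With a true effect, both models gave the same mean estimate, about 8.8. Leaving out baseline does not distort the test.

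**Step 3: what adjustment would gain.** To a first approximation the SE is multiplied by √(1 − r²): 0.98, 0.95 and 0.87 at r = 0.2, 0.3 and 0.5. This was checked by simulation: 40,000 replicates, 49 + 48 patients, t-test on 95 df against ANCOVA on 94 df, centre effect not simulated. Assumptions: baseline N(57, 17) restricted to 0–75, where 57 is 74.73 − 18 rounded and the SD of 17 is assumed. That gives a baseline mean of 52.5 and SD of 13.6. The correlation r is to the outcome before capping.

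| r (assumed) | Power, unadjusted | Power, adjusted | 95% CI half-width, unadjusted | 95% CI half-width, adjusted |
|---|---|---|---|---|
| 0 | 80.5% | 79.9% | 6.09 | 6.13 |
| 0.2 | 80.0% | 81.2% | 6.10 | 6.01 |
| 0.3 | 79.9% | 83.3% | 6.11 | 5.86 |
| 0.5 | 79.7% | 89.2% | 6.14 | 5.34 |

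At r = 0.1 power goes from 80.0% to 80.2%, and at r = 0.4 from 80.2% to 86.1%.

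**Step 4: chance baseline imbalance.** The SD of the difference in mean baseline KOOS is 13.6 × √(1/49 + 1/48) = 2.76 points. A one-SD difference moves the unadjusted estimate by r × SE: 0.2 × 3.07 = 0.6, 0.3 × 3.08 = 0.9 and 0.5 × 3.10 = 1.5 KOOS points.

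**Step 5: the interaction model.** If a share p of patients is in the reference onset category, the SE of the therapy coefficient is about 1/√p times the overall SE: 1.41 at p = 0.5 and 1.83 at p = 0.3. That coefficient cannot stand in for an overall effect.

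**Step 6: disease duration.** Blocks of 2, 4 and 6 in five centres, 108 patients, 40,000 replicates. The arms differ in acute share by 10 or more percentage points in 25.8%, 28.4% and 29.3% of trials if 30%, 40% and 50% of patients are acute (assumed shares). If onset is worth 5 to 10 KOOS points (assumed), a 10-point imbalance shifts the estimate by 0.10 × 5 = 0.5 to 0.10 × 10 = 1.0 point.

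**The case against.** The strongest reply is that this is a preference for efficiency. The primary model matches the t-test used for sizing, it is unbiased, and it reaches its power. A simple primary model with an adjusted sensitivity analysis is a legitimate design. All of that stands, and it is why the point is not about validity.

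The gain also rests on an r that the documents do not give. The baseline limit of 75, the ceiling at 24 months and questionnaires up to six months old before biopsy may all weaken it. That stands too: at r of 0.2 or less the gain is negligible. The trade is still lopsided, at about 0.6 points of power lost if r = 0 against 3 to 10 gained at r = 0.3 to 0.5.

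Two specified analyses of 24-month KOOS already adjust for baseline, and SAP 4.2 requires an effect measure with a 95% CI for every test. But SAP 4.2 does not say how the interaction model averages over onset, and SAP 7.3 reports a median difference. The ceiling is a reason to look at medians. It does not invalidate a mean model, as the type I error in step 2 was obtained with the cap in place.

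The comparison with the secondary endpoints is clear for KOOS and EQ-5d. It is weaker for MOCART and dGEMRIC, for which no baseline score is described.

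On allocation, randomisation does prevent systematic confounding with disease duration. Protocol 6.2.1 nevertheless credits the blocks with it, and they do not balance duration.

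Finally, another analysis added after outcomes were seen leaves room for selective emphasis. This is a real cost, and it is why the adjusted model must not displace the primary one.

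**Conclusion.** The concern holds, as an improvement that should be made rather than an error that invalidates the trial. The unadjusted primary analysis is valid and correctly sized. It forgoes precision that costs one degree of freedom to obtain: nothing useful at r of 0.2 or below, about 3 points of power at r = 0.3 and about 10 at r = 0.5, with the CI half-width falling by about 0.25 and 0.8 KOOS points at the last two values. These sizes depend on the assumed r and baseline SD and on a simulation without centre effects. Independently of r, the plan leaves the baseline-adjusted overall mean difference unspecified, and Protocol 6.2.1 claims more for the blocks than they deliver. The effect of the latter on the estimate is small under the assumptions shown.

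**What to change.** **In a plan still open to change:** make the primary model therapy plus continuous baseline KOOS, centre random, no interaction. Add onset as a main effect only once its cut-off is settled. It is one year in the synopsis, Protocol 3.1 and 11.4.2 and SAP 6.1 and 6.3.1, but the lay summaries use two years and Protocol 9.2.3 has "acute (onset < 2 years) or chronic (onset > 2 years").

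**For this SAP, which already describes the observed 24-month distribution:**

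- Keep the pre-specified unadjusted model as primary.
- Report the main-effects adjusted model beside it with its 95% CI, labelled post hoc and supportive.
- For the interaction model in 6.3.1, name the overall contrast, for example the therapy effect averaged over the observed onset shares.
- Correct Protocol 6.2.1 to say that permuted blocks per centre balance arm sizes within centre only and do not prevent imbalance in disease duration.

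**Cost:** no new data; one model, one contrast and one sentence. Each covariate uses one degree of freedom, and the adjusted result carries its post hoc label. Baseline KOOS should be nearly complete, though SAP 6.4 allows for gaps in the imputation variables.

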Recent studies have indicated that 'acute' cartilage lesions have a more favorable prognosis following cellular therapy than those defined as 'chronic'. Although a threshold time to distinguish between acute and chronic defects after onset of the traumatic event has not yet been defined, there is increasing consensus on the fact that 2-3 years after the trauma the joint starts displaying homeostatic changes and possible traits of early degeneration. On one hand, a more mature cartilage graft, due to the higher mechanical stability and superior cell protection, could play a critical role in the repair of chronic cartilage lesions. On the other hand, an immature graft could be sufficient to trigger anabolic regenerative processes in the case of acute defects. Therefore, it is necessary to compare efficacy of N-TEC and N-CAM in the clinical settings of acute (defined as <1 years) vs chronic (defined as >1 and

Document:	Clinical Study Protocol
Version:	V07
Page number:	31 of 80
Acronym	Nose to Knee II

< 5 years) cartilage lesions. This analysis will be performed retrospectively.

=> determine whether the efficacy of each treatment has a correlation to the characteristics of the defect (e.g. "acute" versus "chronic" setting) possibly allowing the most promising treatment in relation to the time after the initial cartilage injury (onset of symptoms) to be selected

	Therapy	Grafted material	Advantages	Disadvantages
	Spherox [®]	Spheroids of human autologous matrix-associated chondrocytes for implantation suspended in isotonic sodium chloride solution.	 Only autologous cells implanted (no scaffold) Arthroscopic implantation possible 	 Variability of ACs Cells directly exposed to inflammatory and mechanical assaults (self-synthesizing extracellular matrix) Issues linked to cell retention in the defects Long rehabilitation protocol
Existing tissue engineere d products	*MACI [®] (Matrix-induced autologous chondrocyte implantation)	autologous AC seeded in collagen type I/III membrane	 Better retention of cells in the defect Initial mechanical stability Partial chondrogenic re-differentiation 	 Rather fibroblastic cell phenotype in repair tissue Variability of ACs Possible foreign body reaction to the scaffold Cells directly exposed to inflammatory and mechanical assaults (no newly formed extra-cellular matrix) Long rehabilitation protocol

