11.2 Determination of Sample Size

Sample size was estimated to be such that it would be able to show the superiority of N-TEC to N-CAM regarding the primary endpoint. Assumptions for sample size calculation were based on a study (Saris et al., 2008), in which an increase in a mean overall KOOS score after 18 months of 18 points to a final value of 74.73 with a standard deviation of 17.01 was reported. We have assumed that the effect size after 24 months will be at least as big.

Sample size was calculated using a resampling method. Each sample size ($n_i=1,...,21=40,...,160$) was evaluated by sampling R = 999 times, $n_i/2$ KOOS scores from a normal distribution with $\square=75$ and $\square=17$ for the N-CAM group, and $n_i/2$ KOOS scores from a normal distribution with $\square=75+\square$ and $\square=17$ for the N-TEC group. The size of \square was varied between 5 and 15. Values that exceeded 100 were set to 100.

N-CAM and N-TEC were tested for a difference in KOOS score using a two-sided t-test. Superiority of N-TEC to N-CAM was declared when the test showed a significant result. Sample size was set to ensure at least 80 % power (1 - \square = 0.8), at a significance level of \square = 5 %.

For this study, 108 patients should be recruited to ensure 97 evaluable patients at a power of 80%, considering an overall drop-out rate of 10% (Figure 11.2.1).

[figure not shown]

Fig. 11.2.1: Sensitivity of the sample size with regard to absolute difference in KOOS after 24 months (N-TEC vs. N-CAM), assuming a mean KOOS of 75 for N-CAM. An example is given based on an expected absolute difference of 10 score points (Curves are smoothed and are for illustrative purpose only)

Document:	Clinical Study Protocol
Version:	V07
Page number:	63 of 80
Acronym	Nose to Knee II

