11.4.2 Primary Analysis

The primary objective is to demonstrate in patients younger than 65 years with articular knee cartilage injuries the superiority of N-TEC to N-CAM, assessing by KOOS measured 24 months after surgery.

The primary endpoint will be analyzed with a linear mixed effects model, including therapy (N-TEC vs. N-CAM; categorical variable) as single explanatory variable (fixed effect), and including study center as random effect variable to account for the multicenter study design.

Sensitivity analyses: As a sensitivity analysis, we will analyze the primary endpoint by adjusting for covariates and testing for interactions. The linear mixed-effects model will include therapy (N-TEC vs. N-CAM; categorical variable), onset of symptoms (stratified categorical: acute: <= 1 years; chronic: > 1 years) and the covariate baseline KOOS (continuous variable) as explanatory variables (fixed effects). In addition, the model will include the interaction between therapy and onset of symptoms. A significant interaction would indicate that the outcome of the therapy depends on how long the symptoms have been present. Further, study center will be included as a random effect variable in the model to account for the multicenter study design.

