2.3. Sample size

The primary endpoint is the Knee injury and Osteoarthritis Outcome Score (KOOS) measured 24 months after surgery. The score ranges from 0–100; the higher the score, the better the outcome. The null hypothesis is that there is no difference in the primary endpoint between N-TEC and N-CAM ($H_0 : KOOS_{N-TEC} - KOOS_{N-CAM} = 0$). The alternative hypothesis is that N-TEC and N-CAM differ significantly in terms of the primary endpoint ($H_A : KOOS_{N-TEC} - KOOS_{N-CAM} = \delta \neq 0$). An absolute difference (δ) of 10 score points or more is considered clinically relevant. These hypotheses will

determine whether the primary objective, namely that therapy with a mature graft will improve the clinical efficacy for the patient, is met.

Sample size was estimated to be such that it would be able to show the superiority of N-TEC to N-CAM regarding the primary endpoint. Assumptions for sample size calculation were based on a study, in which an increase in a mean overall KOOS score after 18 months of 18 points to a final value of 74.73 with a standard deviation of 17.01 was reported¹. We have assumed that the effect size after 24 months will be at least as big. Sample size was calculated using a resampling method. Each sample size ($n=1, \dots 160$) was evaluated by sampling $R = 999$ times, $n/2$ KOOS scores from a normal distribution with $\mu = 75$ and $\sigma = 17$ for the N-CAM group, and $n/2$ KOOS scores from a normal distribution with $\mu = 75 + \theta$ and $\sigma = 17$ for the N-TEC group. The size of θ was varied between 5 and 15. Values that exceeded 100 were set to 100. N-CAM and N-TEC were tested for a difference in KOOS score using a two-sided t-test. Superiority of N-TEC to N-CAM was declared when the test showed a significant result. Sample size was set to ensure at least 80 % power ($1 - \beta = 0.8$), at a significance level of $\alpha = 5\%$. For this study, 108 patients should be recruited to ensure 97 evaluable patients at a power of 80%, considering an overall drop-out rate of 10%.

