4.2. Confidence intervals and p-values

The statistical testing will be two-sided with a significance level of 5%. All tests will be accompanied by an effect measure (N-TEC vs N-CAM) with a 95% confidence interval (95% CI).

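### Symptom duration is modelled only as acute or chronic at 1 year, a cut the protocol calls undefined and contradicts elsewhere; a continuous duration-by-therapy term should be added beside it

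*SAP*

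**What the plan says.** Protocol 11.4.2 and SAP 6.3.1 describe the same sensitivity model for the primary endpoint. Its fixed effects are therapy, baseline KOOS as a continuous covariate, and "onset of symptoms (stratified categorical: acute: <= 1 years; chronic: > 1 years". The SAP continues: "In addition, the model will include the interaction between therapy and onset of symptoms". Both documents say that a significant interaction would mean the result of therapy depends on how long symptoms have lasted.

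Protocol 11.4.3 and SAP 6.3.1.2 carry this specification over to KOOS at 12 months, dGEMRIC, MOCART and EQ-5D. The exploratory onset analysis (Protocol 9.2.3, SAP 6.1) also uses two classes. No continuous, spline or multi-category analysis of duration is planned.

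On the cut itself, Protocol 3.1 concedes: "Although a threshold time to distinguish between acute and chronic defects after onset of the traumatic event has not yet been defined". It places the onset of joint changes at 2 to 3 years, then adopts 1 year. The synopsis, Protocol 11.4.2, SAP 6.1 and SAP 6.3.1 use 1 year. The study summary and Protocol 9.2.3 use 2 years.

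**The concern.** The question is how the graft effect varies with time since onset, and Protocol 4.1 makes treatment selection by that time part of the overall objective. A two-class factor answers it coarsely. A patient with 13 months of symptoms is grouped with one of several years' duration and separated from one with 11 months. The current eligibility list in Protocol 7.1 sets no upper limit on duration, although Protocol 3.1 describes chronic as more than 1 and less than 5 years.

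Nothing in the design forces the split. SAP 2.2 stratifies randomisation by centre only, so the word "stratified" in the model description does not refer to a randomisation stratum. The trial was also sized for a main effect, so the interaction has little information to spare. If the dependence on duration is gradual, the split may miss an interaction that the same data could show.

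**Working it through.** **1. The plan's own figure.** The test is described as follows: "The statistical testing will be two-sided with a significance level of 5" per cent. Other inputs come from Protocol 11.2 and SAP 2.3: N-CAM mean 75, a 10-point difference ("An example is given based on an expected absolute difference of 10 score points"), SD 17 ("to a final value of 74.73 with a standard deviation of 17.01 was reported"), 1:1 allocation, 80% power, and a ceiling ("Values that exceeded 100 were set to 100").
- Uncapped normal formula: 2 × (1.960 + 0.842)² × 17² / 10² = 45.4, so 46 per arm and 92 in total.
- Simulating the plan's capped method (100,000 runs) gives 80.2% power at 48 + 49 = 97.
- Dropout: 97 / 0.90 = 107.8, so 108.

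The plan's 97 and 108 reproduce. The documents give no power figure for the interaction.

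**2. Information kept by a split.** Relative to a linear continuous term, a two-class split keeps the squared correlation between duration and the class indicator. If the scale on which the effect is linear is normally distributed, for example log duration, this is φ(z_p)² / [p(1 − p)], where p is the share in one class. The documents do not give p, so a range is shown.

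| Smaller class | Kept | Lost | 97 patients count as |
|---|---|---|---|
| 50% | 0.3989² / 0.25 = 0.637 | 36% | 62 |
| 40% | 0.622 | 38% | 60 |
| 30% | 0.3477² / 0.21 = 0.576 | 42% | 56 |
| 20% | 0.2800² / 0.16 = 0.490 | 51% | 48 |
| 10% | 0.342 | 66% | 33 |

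**3. Other distributions, with the effect linear in raw years and the cut at 1 year.**
- Uniform on 0 to 5 years: kept = 3p(1 − p) = 3 × 0.2 × 0.8 = 0.48, so 52% is lost.
- Exponential with mean m years: kept = (1/m)² × P/(1 − P), with P = exp(−1/m). For m = 1, 2 and 3 this gives 0.58, 0.38 and 0.28, so 42%, 62% and 72% is lost.
- Log-normal, uncapped, median 0.5 to 3 years and SD of log duration 0.7 to 1.3: about 41% to 95% is lost.

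**4. Power of the interaction test.** Simulation with 97 patients, 1:1, residual SD 17, ordinary least squares and 6,000 runs. Log duration is standard normal, so the 2-year point lies ln 2 = 0.69 SD above the 1-year point. The effect sizes are assumptions.

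| True pattern | Smaller or acute share | Continuous term | 1-year split |
|---|---|---|---|
| Linear, 9.9 points per SD of log duration | 50% | 78% | 60% |
| | 35% | 78% | 57% |
| | 20% | 79% | 47% |
| 20-point step at 1 year | 50% | 61% | 81% |
| | 20% | 35% | 61% |
| 20-point step at 2 years | 35% | 56% | 33% |

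Even in the split's best case (a step at 1 year, equal classes), about 81% power needs the class-specific graft effects to differ by 20 points. That is twice the 10-point main effect the trial was sized for.

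**The case against.** The strongest reply is that acute versus chronic is the clinical question the protocol poses, that the split was pre-stated in Protocol 11.4.2, and that the size of any loss rests on inputs the documents do not give. Much of this stands. If the effect truly changes at 1 year, the split loses nothing and outperforms the continuous term. A linear relation in log duration is itself an assumption. It treats the change from 3 to 6 months like that from 3 to 6 years, and nothing in the documents supports this.

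Three stronger readings are tempting and are not supported.
- A reader might infer that the split certainly discards a third to a half of the information. That range is conditional on the assumptions in step 2.
- A reader might infer from Protocol 3.1 that joint changes develop gradually. The section says only that they begin at 2 to 3 years, which is at least as compatible with a threshold. It gives no evidence for one at 1 year.
- A reader might infer that the split should be replaced. SAP 7.3 shows that the 24-month KOOS distribution had been inspected by arm, so demoting a pre-stated interaction in favour of a new functional form would be a post hoc switch.

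What the objection does not answer is that the interaction is interpreted as dependence on length of symptoms, while it is tested at a single cut on which the documents disagree.

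**Conclusion.** The point holds in conditional form. Duration is used only as two classes, at a cut the protocol says is undefined and sets at 2 years elsewhere. If the effect is linear in log duration, log duration is roughly normal and the smaller class holds 20% to 50%, about 36% to 51% of the information on the interaction is lost. Across the other patterns examined, the loss runs from 0% (a true step at 1 year) to well above half (skewed durations).

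The scope is the sensitivity model, the modelled secondary endpoints and the exploratory onset analysis. A reader might infer that the primary result is affected. It is not, because the primary model in SAP 6.3.1 has therapy as its only fixed effect. In the adjusted models, variation in duration within a class costs precision; under randomisation it does not bias the treatment estimate. Treatment failure and the KOOS sub-scores added in SAP 7.2 have no stated model, and the median regression in SAP 7.3 does not mention onset, so the point does not extend to them.

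**What to change.** 1. Reconcile the acute/chronic cut across the synopsis, study summary, Protocol 3.1, 9.2.3 and 11.4.2, and SAP 6.1 and 6.3.1. Keep the pre-stated split and its interaction.
2. Add to SAP 6.3.1 and 6.3.1.2 a supplementary model with log(months since onset) as a continuous covariate and its interaction with therapy, other terms unchanged.
3. Report the N-TEC minus N-CAM difference with 95% CI at fixed durations, for example 6, 12, 24 and 60 months, within the range observed. Check linearity with a quadratic or spline term.
4. Label the model supplementary and post hoc, because outcome data had been seen when the SAP was written.

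The cost is SAP wording and one more exploratory model with an assumed functional form. It needs no new data if onset timing was recorded. The planned retrospective classification in Protocol 9.2.3 implies that it was, but the eCRF list in Protocol 12.1.1 names only history of injury. The sponsor must confirm that timing, and not just the class, is in the database.
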